6.5 Randomisation

Participants will be randomised as close to the planned operation as possible (ideally 30 minutes before the participant is taken to theatre), after consent has been given, baseline assessments have been completed and eligibility has been confirmed by the Principal Investigator, a delegated medically qualified doctor or Advanced Nurse Practitioner who has undergone suitable training.

Participants will be allocated in a 1:1 ratio to either CDI plus standard de-airing or medical air insufflation (placebo) plus standard de-airing. The allocation will be computer-generated and will be stratified by centre, type of procedure (i.e. valve only or valve combined with another procedure e.g. CABG) and whether planned surgical access is minimally invasive (e.g. thoracotomy), by an independent BTC CTEU statistician, not involved in the study, before recruitment begins.

Randomisation will be performed using a secure internet-based randomisation system ensuring allocation concealment by a member of the research team not involved in data collection or participant follow-up.

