11.1 Sample size calculation

11.1.1 Main trial

The target sample size is 704 participants, 352 per group, which will provide 90% power at a 5% significance level (2-sided) to detect a 25% relative reduction in the incidence of post-operative cerebral infarcts with CDI, assuming a 48% rate in the placebo group. Missing data for the primary outcome is expected to be minimal as the DW MRI brain and assessment of stroke will be completed prior to the participant's discharge home.

Data from our systematic review and meta-analysis (21) showed a 43% relative risk (from 21% to 12%) reduction in the incidence of neurocognitive decline with CDI. It also showed a 47% relative risk reduction in the incidence of stroke over time following the introduction of CDI in Bristol in 2006 from 3.4% in 2005 to 1.6% in 2008. This was estimated from research data on 1754 valve surgeries and 42 strokes. This provided the basis for the target effect size; it is less than the effect observed in our systematic review, which is likely to have overestimated the treatment effect based on small RCTs at unclear or high risk of bias.

The anticipated event rate in the placebo group was chosen based on a meta-analysis of all available observational studies where brain MRI was routinely performed early after open heart valve surgery. Eight studies were identified with sample sizes ranging from 15 to 129 participants and rates of new ischemic lesions at MRI ranging from 38% to 72%. The pooled random effects estimate of new ischemic lesions was 55% (95% CI 48% to 63%). Assuming a 48% event rate (the lower limit of the 95% CI) leads to a larger sample size (compared to assuming a 55% event rate).

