11.3 Plan of analysis – primary and secondary outcomes

Analyses will be performed on the intention-to-treat basis and will be directed by a pre-specified statistical analysis plan. Analyses will use data from all patients randomised. Primary and secondary outcomes will be compared using logistic (binary variables), poisson (count variables), Cox proportional hazards (time to event variables), or linear mixed model (continuous variables measured at multiple time points) regression, with placebo as the reference group. Mixed models allow all participants with data to be included in the analysis, i.e. partial missing data (assumed missing at random) is permitted. Interactions between treatment and time will be examined and if significant at the 10% level, results will be reported separately for each post-operative time point; otherwise overall treatment effects will be reported. Model validity will be checked using standard methods; if a model is a poor fit, alternative models or transformations will be explored. Outcomes analysed on a logarithmic scale were transformed

back to the original scale after analysis and results presented as geometric mean ratios. Analyses will be adjusted for baseline values, and stratification variables (centre and type of surgery). Findings will be reported as effect sizes with 95% CIs.

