- 33. Ware J, Jr., Kosinski M, Keller SD. A 12-Item Short-Form Health Survey: construction of scales and preliminary tests of reliability and validity. Med Care. 1996;34(3):220-33.

18. Amendments to protocol

Amendme nt number (i.e. REC and/or MHRA amendmen t number)	Previous version	Previous date	New version	New date	Brief summary of change	Date of ethical approval (NA if non- substantial)
SA1	1.0	29/04/2020	2.0	28/09/2020	Updates to the participant pathway (including remote consent and follow up), surgical guidance, and addition of background safety data.	19/10/2020
SA2	2.0	28/09/2020	3.0	24/11/2020	Updates to the inclusion criteria and randomisation strata.	05/01/2021
SA3	3.0	24/11/2020	4.0	25/05/2021	Update to Chief Investigator details on front page	16/06/2021
SA4	4.0	25/05/2021	5.0	23/09/2021	Updates to eligibility criteria, addition of Advance Nurse Practitioners confirming eligibility. Updates to surgical procedures to allow for wider range of equipment and flow rates to be	17/11/2021

					used, which do not affect the primary outcome data. Updates throughout to add clarity to procedures.
SA5	5.0	23/09/2021	6.0	Xx/11/202 1	Updated research team. Updated terminology in the dosing schedule from lower to inferior. Updated surgical procedures to include normothermic cardiopulmonary bypass procedures and PaCO2 levels in kilopascals.

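### Randomisation is stratified by three factors, but the adjustment list in section 11.3 names only two and leaves out planned surgical access: a minor mismatch that costs nothing to correct

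*Protocol*

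**What the plan says.** Section 6.5 of the protocol describes a 1:1 allocation that is "stratified by centre, type of procedure (i.e. valve only or valve combined with another procedure e.g. CABG". It then adds a third factor, "whether planned surgical access is minimally invasive (e.g. thoracotomy".

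Section 11.3 assigns a model to each kind of outcome: "Primary and secondary outcomes will be compared using logistic (binary variables" comes first, followed by models for counts, times to event and repeated continuous measures. One sentence sets the covariates for all of them: "Analyses will be adjusted for baseline values, and stratification variables (centre and type of surgery". Planned access is not named as an adjustment variable anywhere in the protocol.

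The sample size section (11.1.1) reads "The target sample size is 704 participants, 352 per group", giving "90% power at a 5% significance level (2-sided" for a "25% relative reduction in the incidence of post-operative cerebral infarcts with CDI" from 48% under placebo. That calculation uses no covariates.

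**The concern.** The bracket in section 11.3 reads as the list of stratification variables, and it is one short. Section 11.3 does not defer the covariates to the statistical analysis plan. It promises adjustment for the stratification variables and then names an incomplete set. A later plan would have to depart either from the list in 11.3 or from the design in 6.5. Until this is settled, the primary model has two readings: all the stratifiers, or only the two named.

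Stratifying on a prognostic factor makes the arms more alike than simple randomisation would. A model without that factor still charges for the variation that the design has removed. Its test is then conservative, and some power is given away. A link between access and lesions is conceivable, because section 7.1.2 ties peripheral (femoral) cannulation to minimally invasive procedures and otherwise describes cannulation of the ascending aorta. The protocol does not claim that access predicts lesions.

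**Working it through.** **Step 1. Compare the two lists.**

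| Factor | Section 6.5 (design) | Section 11.3 (analysis) |
|---|---|---|
| Centre | yes | yes |
| Type of procedure: valve only or combined | yes | yes, as type of surgery |
| Planned access minimally invasive | yes | not listed |

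Three factors in the design against two in the analysis.

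**Step 2. Reproduce the sample size.** Inputs from 11.1.1: p1 = 0.48; p2 = 0.48 × 0.75 = 0.36; difference 0.12; two-sided 5%; power 90%; 1:1. With the pooled variance under the null,

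n = [1.960 × √(2 × 0.42 × 0.58) + 1.282 × √(0.48 × 0.52 + 0.36 × 0.64)]² / 0.12² = 353.4, so 354 per group.

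With the unpooled variance, n = (1.960 + 1.282)² × 0.48 / 0.0144 = 350.2, so 351. The stated 352 lies between the two, and its power with the pooled formula is 0.899. The calculation uses no covariates, so it does not depend on this point.

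**Step 3. Effect on the test under the null.** The protocol gives neither the share with minimal access (call it π) nor its odds ratio for lesions, so both are assumed. Hold the overall rate at 48% and let a and b be the lesion rates with conventional and minimal access. Stratification removes the between-access variance π(1 − π)(b − a)² from the treatment comparison. A model without access still uses the full 0.48 × 0.52 = 0.2496. With R the ratio of these two variances, the true standard deviation is √(1 − R) times the reported standard error, and the actual rejection rate is 2 × [1 − Φ(1.960/√(1 − R))].

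| Assumed π, odds ratio | a, b | R | √(1 − R) | Rejection under the null |
|---|---|---|---|---|
| 30%, 2 | 0.429, 0.600 | 0.00617/0.2496 = 0.025 | 0.988 | 4.7% |
| 30%, 3 | 0.400, 0.667 | 0.01493/0.2496 = 0.060 | 0.970 | 4.3% |
| 40%, 3 | 0.373, 0.641 | 0.01722/0.2496 = 0.069 | 0.965 | 4.2% |

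Simulation agrees: 4.2–4.7% without the term and 4.9–5.2% with it.

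**Step 4. Effect on power.** The odds ratio across all patients is (0.36/0.64)/(0.48/0.52) = 0.609, with log −0.495 and reported standard error √[(1/0.2496 + 1/0.2304)/352] = 0.154. With 30% minimal access and an odds ratio of 3:

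- Without access, the true standard deviation is about 0.149, so power = Φ[(0.495 − 1.960 × 0.154)/0.149] = 0.90.
- With access, the conditional odds ratio is 0.590 (log −0.528) and its standard error 0.159, so power = Φ(0.528/0.159 − 1.960) = 0.91.

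Simulation with access exactly balanced by arm, 704 patients and 6,000 runs per scenario gives the following.

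| Assumed π, odds ratio | Power without access | Power with access |
|---|---|---|
| 10%, 2 | 0.909 | 0.909 |
| 30%, 2 | 0.906 | 0.907 |
| 30%, 3 | 0.908 | 0.918 |
| 40%, 3 | 0.909 | 0.917 |

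The two models reached different conclusions in under 1% of simulated trials. A separate simulation (1,500 runs per scenario) used permuted blocks within 8 centres, 2 procedure types and 2 access types. It also found a gain of at most about 1 point.

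**The case against.** The strongest defence is that the intent in 11.3 is already right, since it says the stratification variables will be adjusted for. The bracket may be loose shorthand in which type of surgery is meant to include access. The amendment log in section 18 records, for version 3.0, "Updates to the inclusion criteria and randomisation strata", so the bracket may simply not have been updated when the strata changed. The intent does count in the plan's favour. The shorthand reading is weak, because 6.5 defines procedure type by whether another procedure is combined and names access separately. The amendment history is only an inference, and the mismatch in the current text does not rest on it.

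The defence is right about size. Three stronger readings are tempting, and the documents do not support them.

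- A reader might infer that the omission pulls the trial below its planned 90% power. With the planned rates held, power without the term stays at about 90–91%.
- A reader might take the odds ratio of 0.61 without access, against 0.59 with it, as a bias that adjustment removes. The two are a marginal and a conditional odds ratio, which differ even under perfect balance (non-collapsibility). Nor does adding access shrink the standard error of the log odds ratio. It rises from 0.154 to about 0.16, and the small gain comes from the larger conditional effect.
- A reader might argue that access must matter because de-airing differs. Section 7.1.3 gives one de-airing description and does not distinguish by access.

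The protocol also gives no count of minimally invasive cases by centre, so sparse cells might be feared. The proposed change is one binary main effect, not a centre-by-access term, and even at an assumed 10% it would rest on about 70 of 704 patients.

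**Conclusion.** The mismatch is real and is in the current protocol: the design stratifies by three factors and the analysis lists two. It is a minor consistency error, and correcting it is a free improvement. It does not threaten the trial's conclusion.

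If planned access predicts lesions, leaving it out makes the test slightly conservative and loses at most about 1 point of power. That figure assumes an access odds ratio of 3 with 30–40% minimal access. At an odds ratio of 2 the loss is negligible, and if access is not prognostic there is none. The omission cannot inflate type I error, and 704 remains the right number under the plan's own assumptions. The better reason to correct it is that the primary model should have one reading before anyone sees comparative data.

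**What to change.** Amend the covariate sentence in section 11.3 to say: *adjusted for baseline values and all stratification variables (centre, type of procedure, and planned surgical access as recorded at randomisation)*. Use the planned access entered at randomisation, not the access actually used, so that the covariate is the one that was stratified on and cannot be affected by later events. If access is to be left out deliberately, say so and give the reason. Carry the same list into the statistical analysis plan, and make the change before any comparative analysis.

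The cost is one line of text and one extra model parameter. The factor should be on record for every participant, because it is needed to randomise, so no new data, patients or sample size calculation are required.

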2.1 Brain injury and dysfunction after cardiac surgery

Brain injury and dysfunction is a common complication after cardiac surgery and significantly increases the likelihood of patients requiring long-term care. Peri-operative stroke occurs in 2-6% of all patients (1). More than 20% of patients over 65 years of age and 33% of patients over 80 years of age experience post-operative delirium (1, 2). Post-operative cognitive dysfunction is estimated to affect more than 80% of patients at discharge, and persist in 25% of all patients at 1 year (3). Brain injury may also trigger chronic or progressive dementia (4).

It is assumed that brain injury is triggered by the release of microemboli (microscopic atherosclerotic particles or air bubbles) in the blood stream, which are carried to the brain. Indeed, intraoperative transcranial doppler (TCD) ultrasound monitoring demonstrates showers of small particulate or air emboli during cardiac and vascular manipulations (5). However, the relationship between intraoperative brain embolic load and brain injury still needs to be clarified. Some studies have reported that the embolic burden detected by TCD monitoring is associated with early cognition deficits while others have not confirmed this finding (6, 7).

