2.2 Magnetic resonance imaging (MRI) to detect perioperative brain injury

MRI examination of the brain is the "gold standard" for identifying and quantifying peri-operative brain injury (8) and has been used widely in randomised controlled trials (RCTs) investigating neuroprotective interventions in cardiac surgery (9-11). A variety of imaging techniques are applied to identify markers of such injury, including diffusion weighted imaging (DWI). The main advantage of DWI is that lesions typically appear within 2 hours of surgery and disappear after two weeks, therefore, new acute lesions represent "new" injury, so a baseline scan is not required to confirm that the lesion was not present before surgery. Another advantage is that the new framework for defining stroke proposed by the American Heart Association/American Stroke Association (8) includes neuroimaging (together with clinical or pathological evidence), so lesions found on DWI count as "silent" brain injury even in the absence of obvious clinical findings.

DWI lesions following left heart valve surgery are reported in about 50% of patients (5, 9). These lesions are multiple and very small (1-10mm in diameter and 32-750mm³ in volume). They are located in all cerebrovascular territories, but more frequently in frontal and watershed border zones and the pattern of distribution confirms an embolic basis. Few (\sim 9%) are associated with overt clinical signs of stroke so they represent "silent" brain injury in most cases (5, 9).

In population-based studies, a strong association has been found between "silent" brain injury identified by MRI and prevalent cognitive dysfunction and dementia (12-14), therefore it is plausible that a similar relationship exists between the appearance of new lesions after cardiac surgery and neurocognitive decline. Some preliminary data has suggested that the appearance of new "silent" brain lesions after cardiac surgery is associated with early post-operative

neurocognitive deterioration (15) although further investigations with longer follow-up are needed.

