2.4 Review of existing evidence

We have conducted and recently published a systematic review and meta-analysis of all available RCTs investigating the efficacy of CDI versus standard de-airing techniques (21). Outcomes investigated were post-operative stroke, neurocognitive dysfunction, and in-hospital mortality. Pooled estimates were obtained using random-effects models to account for clinical diversity and methodological variation between studies. Eight RCTs were identified comparing CDI vs. standard de-airing but only four studies reported on the incidence of post-operative neurocognitive decline (23-25); 283 randomised to CDI, 284 randomised to standard de-airing. Most studies were small (<100 patients) and at high risk of bias. Type and timing of neurocognitive function tests varied among studies. Different methods were used for delivery of carbon dioxide. In-hospital mortality was 2.1% vs 3.0% in the CDI and standard de-airing (control) groups, respectively (risk difference (RD) 0%; 95% CI -2% to 2%. Incidence of stroke was 1.0% vs 1.2% (RD 0%; 95% CI -1% to 2%) and neurocognitive dysfunction was 12% vs 21% (RD: -7%; 95% CI -0.22% to 8%) in the CDI and control group, respectively. The results of the meta-analysis were influenced by our decision to include a trial with no events (23), which resulted in a more conservative estimate of treatment effect. Excluding this trial from the analysis suggested a protective effect of CDI on neurocognitive function (OR 0.46, 95%CI 0.22 to 0.96).

3. Rationale

Nearly 40,000 people in the UK (http://bluebook.scts.org/) and many more worldwide have cardiac surgery annually. Ischaemic brain injury represents a common complication and is associated with increased hospital stay, slow recovery, poor quality of life, further health care resource use and reduced long term survival. Cardiac surgery is increasingly being offered to older, higher-risk patients with comorbidities, so the incidence of neurological complications is likely to increase in the future. CDI is a widely used intervention, which many surgeons believe improves neurological outcomes. However, there is little evidence for its efficacy or risk of harm and its routine use is not recommended and surgeons are currently in equipoise regarding its adoption.

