7.2 Duration of treatment period

The duration of the treatment commences when the patient enters the operating room and concludes when the patient leaves the operating room after their surgery.

The duration of the procedure is expected to be between 2 hours and 4 hours.

Table 1 Schedule of assessments

			Post-surgery				
	Baseline	Intraoperative	Day 3 (between 3-5 days post op)	Day 2 – 7 (but no more than 10 days)	Discharge	Routine post-op follow-up	Three- month follow up
National Institutes of Health Stroke Scale	✓		✓				✓
Confusion Assessment Method	✓		✓				✓
Functional status: Barthel Index score	✓						✓
Neurocognitive function tests: Addenbrookes Cognitive Examination III and oral Trail Making Tests A&B	✓						√
Quality of life questionnaire (SF-12)	✓						✓
Assessment of post-operative complications					✓		
DW MRI brain				✓			
Assessment of serious adverse events (from randomisation to three month follow up), including readmissions			√	√	√	√	✓
Assessment of blinding success							✓
Transcranial doppler ultrasound*		√					
Near-infrared spectroscopy*		✓					

^{*100} patients at the Bristol centre only

8. Data collection

Each patient will be assigned a unique study number. All data recorded on paper relating to the participant will be located in CRF folders, which will be stored securely. Staff with authorisation to make changes to the study records, including the study database, will be listed on the study delegation log maintained at each centre.

Screening data will be collected for all patients undergoing open heart valve surgery considered for the study. Age, sex and Index of Multiple Deprivation (IMD) will be collected for all patients irrespective if they decline to participate. This information is collected to assess any difference in the patients that do not take part compared to patients that do, to establish if there are any socioeconomic barriers to participation.

Baseline data will be collected after consent. Consenting patients will be contacted by an authorised member of the local research team (as specified in the delegation log) who will provide the opportunity to understand the nature, significance, implications and risks of the trial so that they may make an informed decision if they should take part. If the patient decides to take part the member of the local research team will obtain informed consent.

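### For a primary outcome with no pre-operative scan, section 11.3 adjusts for no patient-level covariate beyond the stratification factors; adding age would recover a little precision at almost no cost

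*Protocol*

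**What the plan says.** Section 11.3 gives a single rule for all primary and secondary outcomes: "Analyses will be adjusted for baseline values, and stratification variables (centre and type of surgery"). It defers further detail to a pre-specified statistical analysis plan, which is not at hand.

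Section 5.1.1 defines the primary outcome as binary: a new lesion on diffusion-weighted MRI, or clinical evidence of permanent brain injury, within 10 days of surgery. On the scan, section 2.2 reasons that acute lesions are new by nature, "so a baseline scan is not required to confirm that the lesion was not present before surgery". Table 1 schedules the scan only after surgery.

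Section 6.5 stratifies randomisation by centre, by procedure (valve alone or combined with another operation) and by whether minimally invasive access is planned. Age is not a stratifier.

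On age, section 8 says: "Age, sex and Index of Multiple Deprivation (IMD) will be collected for all patients irrespective if they decline to participate". Section 3 refers to surgery being offered to "older, higher-risk patients with comorbidities, so the incidence of neurological complications is likely to increase in the future". Section 2.1 states: "More than 20% of patients over 65 years of age and 33% of patients over 80 years of age experience post-operative delirium".

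**The concern.** A rule that adjusts for baseline values works where the outcome is also measured before surgery, as with the Barthel Index, the cognitive tests and SF-12. It has nothing to act on for the imaging part of the primary outcome. For delirium a baseline Confusion Assessment Method result exists. It should vary little, because patients unable to give written informed consent are excluded (6.4.2).

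The primary model is then left with treatment and the stratification factors. In a logistic model, adjusting for a prognostic baseline variable raises power and corrects for chance imbalance in it. Age is the obvious candidate: it is known for every participant, it ranges upward from 50 with no upper limit, and the protocol presents older patients as being at higher neurological risk. At stake is a modest gain on the outcome for which the trial is sized. The validity of the comparison is not in question.

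**Working it through.** **Inputs from the protocol.** Section 11.1.1 plans 352 patients in each arm (704 in all) for 90% power with a two-sided 5% test. The design effect given there is: "detect a 25% relative reduction in the incidence of post-operative cerebral infarcts with CDI, assuming a 48% rate in the placebo group". Hence 48% with placebo and 0.75 × 48% = 36% with carbon dioxide insufflation. Section 6.5 sets equal allocation.

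**Input that is assumed.** The odds ratio per SD of age for the primary outcome is not in the documents. A range of 1.2 to 2.0 is used, with age treated as standard normal.

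**1. Reproduce the plan's figure.**
- Unpooled variance: n = (1.96 + 1.2816)² × (0.48×0.52 + 0.36×0.64) / 0.12² = 10.51 × 0.48 / 0.0144 ≈ 350.2, so 351 per group and 702 in total.
- Pooled variance: 354 per group, 708 in total.
- Power at 352 per group: 89.9%.

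The stated 704 is reproduced, and it takes no credit for covariates.

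**2. Unadjusted logistic comparison.**
- Target log odds ratio: ln[(0.48/0.52)/(0.36/0.64)] = 0.495.
- Standard error: √[1/(352×0.48×0.52) + 1/(352×0.36×0.64)] = 0.154.
- z = 0.495/0.154 = 3.217; Wald power = Φ(3.217 − 1.960) = 89.6%.

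**3. Add age.** The marginal rates are held at 48% and 36%. The conditional log odds ratio and its standard error come from the expected information of a logistic model with treatment and age. Equivalent N is 704 × (3.217/z)².

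| Assumed odds ratio per SD of age | Conditional treatment odds ratio | Standard error | z | Power | Gain (points) | Equivalent N |
|---|---|---|---|---|---|---|
| 1.0 | 0.609 | 0.154 | 3.217 | 89.6% | 0 | 704 |
| 1.2 | 0.607 | 0.155 | 3.229 | 89.8% | 0.2 | 699 |
| 1.5 | 0.598 | 0.157 | 3.275 | 90.6% | 1.0 | 679 |
| 2.0 | 0.578 | 0.162 | 3.375 | 92.1% | 2.6 | 640 |

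The standard error rises with adjustment, but the log odds ratio rises more, which is where the power comes from.

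**4. Cross-check by simulation** (6,000 trials per scenario, simulation error about 0.4 points). Power moves from 90.7% to 91.3% at 1.5, from 89.9% to 91.5% at 1.75, and from 90.3% to 92.6% at 2.0. Between 1.0 and 1.25 no difference is detectable. The two methods agree on a gain of about 0.6 to 1 point at 1.5 and about 2.5 at 2.0.

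**5. Scale.** Section 10.6 expects under 2% loss before discharge. A full 2% leaves 704 × 0.98 ≈ 690, or 345 per group: z = 3.217 × √(345/352) = 3.184, power = Φ(1.224) = 89.0%, a drop of 0.6 points. At an assumed odds ratio of 1.5, age adjustment would roughly make that good.

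**6. Chance imbalance.** Two standard errors of the difference in mean age is 2 × √(2/352) = 0.151 SD. At an odds ratio of 1.5 this moves the unadjusted log odds ratio by 0.151 × ln 1.5 = 0.061, and 0.061/0.495 = 12% of the target effect. An imbalance this large arises in about 5% of trials.

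**7. Cost in parameters.** Expected primary events under the design assumptions: 352 × (0.48 + 0.36) ≈ 296. One extra parameter is negligible.

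**The case against.** The strongest reply is that nothing here is an error. Section 11.3 is a generic sentence, prognostic covariates are ordinary content for an analysis plan that is not shown, and the sample size does not rely on them. Much of that stands. The protocol does, however, name an adjustment set, so this is a comment on a stated model. If the analysis plan already lists age, 11.3 need only be brought into line.

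A reader might go further than the documents allow in several ways:

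- **That the primary model has no patient-level prognostic factor at all.** Type of surgery differs from patient to patient and is in the model. The protocol does not quantify its prognostic strength, but it does not do so for age either. A broad reading of baseline values could also bring in the baseline stroke scale score, which bears on the clinical-stroke part.
- **That omitting age biases the result or undermines the 90% power.** Randomisation prevents the first. Step 1 shows the stated power without any covariate. The confidence interval already allows for the imbalance in step 6.
- **That the delirium figures give an odds ratio near 2 for age.** (0.33/0.67)/(0.20/0.80) = 1.97, but the over-80 group lies within the over-65 group, and the ratio is not per SD. It cannot be placed on the scale of the table.
- **That section 3 shows age predicts imaging lesions.** It speaks of older patients with comorbidities and of neurological complications in general.
- **That age should enter every model lacking a baseline value.** For survival this is not clearly free. If mortality resembled the 2.1% and 3.0% in-hospital rates in section 2.4 (an assumption for this trial), 352 × (0.021 + 0.030) ≈ 18 deaths would have to support treatment, procedure type and at least eight centres already.

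**Conclusion.** The point holds as a low-cost improvement of minor weight. The stated adjustment gives the imaging part of the primary outcome nothing beyond the stratification factors, while a complete and plausibly prognostic variable goes unused. The loss is one of precision. Its size rests entirely on the assumed strength of age: negligible at an odds ratio of 1.25 per SD or below, and reaching about 2.5 power points, or the information of some 64 participants (704 − 640), only at 2.0. The documents do not say where in that range the truth lies, and they do not rule out the low end.

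**What to change.** In section 11.3, state that the logistic models for the primary outcome and for delirium adjust for age at randomisation as a continuous variable, in addition to the stratification factors. Say also what baseline values means for an outcome with no pre-operative measurement. Settle both before any comparative data are seen, so that the covariate cannot be chosen with the results in view, and carry the same wording into the statistical analysis plan.

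The change takes one or two sentences and no new data. The treatment odds ratio becomes conditional on age as well as on the stratification factors, which the report should say. Do not extend the requirement to survival. The 30-day composite can be left as it is, since the protocol gives no event rate by which to judge the cost there.
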